23.1.2 POOLABILITY

Using the LME modeling approach outlined above, poolability will be evaluated across centers by including a fixed effect for Treatment by Center interaction in the model and applying a likelihood ratio test. If the TxC interaction is significant at α =0.15 a Center effect will be included in the final model and the results will be reported separately by Center. For this analysis, Centers with less than 5 enrolled subjects will be combined into a single virtual center.

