7.3 STUDY CENTERS

This study will be conducted at up to 15 centers in the United States. No center will have more than 20% of the target enrollment.

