9.5.3 RANDOMIZATION

Subjects will be randomized to either the TearCare (i.e. "treatment group") or Warm Compress and Lid Massage (i.e. "control group") using a pseudo-random number generator with subjects enrolled according to a predetermined list. Randomization will

use permuted blocks with random block sizes of 2 or 4. The investigational site will be provided a set of envelopes with randomization assignments. Following randomization, the subject should immediately undergo the applicable procedures described in the sections below.

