12.5.2 PRIMARY EFFECTIVENESS ENDPOINT

The primary effectiveness outcome is the change from baseline in Tear Break-Up Time (TBUT) at the 1 month follow up. TBUT will be analyzed using a linear mixed effects (LME) model. This will allow for the proper incorporation of within-person correlation into the statistical model, and will also allow for adjustment for baseline measurements.

Details of the LME model are provided in the Statistical Analysis Plan (SAP) provided in Appendix C. Hypotheses regarding the primary and secondary effectiveness outcomes are described below in Section 12.6.

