12.5.3 POOLABILITY

Using the LME modeling approach outlined above, poolability will be evaluated across centers by testing a Treatment-by-Center interaction (TxC). If the TxC interaction is significant at α =0.15 a Center effect will be included in the final model and results will be reported separately by Center. For this analysis, Centers with less than 5 enrolled subjects will be combined into a single virtual center.

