12.5.6 EVALUATION OF TREATMENT DURATION

If the primary endpoint is successful at the one month primary time point, then treatment duration will be evaluated using a hierarchical testing procedure. Using data that are obtained at the 3- and 6-month follow-up visits we will again test the primary hypothesis comparing change from baseline Tear Break-Up Time (TBUT) between the treatment and control. We will use the same linear mixed effects (LME) model as in the primary analysis, evaluating each time point separately. The two time points will be tested sequentially, stopping at 3 months if the test fails at that point. Treatment duration will be the maximum time point at which this treatment duration testing succeeds, either 1, 3, or 6 months.

This analysis will not be carried out if the primary 1-month endpoint fails, it is not intended to establish primary effectiveness in the event of study failure at one month.

Note that this analysis will be carried out using data that will be at least partially obtained after the primary database lock. However every effort will be made to maintain the masking of assessors through the 6-month follow-up as described in section 9.7.

This analysis does not affect the type I error for the primary endpoint. The 1- 3- and 6-month TBUT outcomes will likely be highly correlated, however the sequential testing will appropriately control the time-wise type I error rate.

For each secondary endpoint that is successful at the one month time point using the hierarchical testing procedure described in 12.5.5, treatment duration will be evaluated at the 3- and 6-month follow up. Evaluation of treatment duration for the secondary endpoints will be based on sequential testing of 3- and 6-month follow up times separately, in the same manner as for the primary endpoint. Secondary endpoints that fail at the 1-month time point will not be evaluated for treatment duration.

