23 APPENDIX C - STATISTICAL ANALYSIS PLAN

23.1 ENDPOINTS AND ANALYSIS METHODS

23.1.1 PRIMARY EFFECTIVENESS ENDPOINT

The primary effectiveness outcome is the change from baseline in Tear Break-Up Time (TBUT) at the 1 month follow up. TBUT will be analyzed using a linear mixed effects (LME) model. This will allow for the proper incorporation of within-person correlation into the statistical tests, and will also allow for adjustment for baseline measurements.

The linear mixed effects model for TBUT can be written as follows:

$$y_{ij} = \beta_0 + \beta_1 T_i + \beta_2 TBUT_{ij,0} + b_{0i} + \epsilon_{ij}$$

Where

- $TBUT_{ij,0}$ is the baseline TBUT value for subject i, eye j, week 0.
- y_{ij} is the 1 month change from baseline TBUT for subject i, eye j.

$$y_{ij} = TBUT_{ij,4} - TBUT_{ij,0}$$

- T_i is the 0,1 treatment indicator for subject i
- $\beta_0, \beta_1, and \beta_2$ are the fixed effect parameters
- b_{0i} is the random effect (random intercept term) for subject i

$$b_{0i} \sim N(0, \sigma_a^2)$$

ullet ϵ_{ii} is the normally-distributed error term

$$\epsilon_{ij} \sim N(0, \sigma_e^2)$$

• $\{b_{0i}\}$ and $\{\epsilon_{ij}\}$ are independent

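### Center enters the primary TBUT model only through an outcome-dependent interaction screen, which runs at about 0.17 to 0.27 rather than 0.15 under the usual chi-square reference

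*Combined protocol and SAP*

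**What the plan says.** SAP 23.1.1 writes the primary model for one-month TBUT change with an intercept, treatment, baseline TBUT, a random subject intercept and error. There is no center term.

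SAP 23.1.2 checks poolability "by including a fixed effect for Treatment by Center interaction in the model and applying a likelihood ratio test". If the interaction reaches 0.15, "a Center effect will be included in the final model and the results will be reported separately by Center". Protocol 12.5.3 repeats the rule: "a Center effect will be included in the final model and results will be reported separately by Center". Both sections merge centers with fewer than 5 enrolled subjects.

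Other sections bear on the point:
- SAP 23.1.3 says the primary analysis uses maximum likelihood.
- Protocol 7.3 allows up to 15 sites and adds "No center will have more than 20% of the target enrollment", so there are at least 5.
- Protocol 9.5.3 uses permuted blocks of 2 or 4 and says "The investigational site will be provided a set of envelopes with randomization assignments". This suggests lists by site but does not state it.
- Protocol 12.5.6 carries the model to 3 and 6 months: "We will use the same linear mixed effects (LME) model as in the primary analysis, evaluating each time point separately".
- Protocol 12.5.2 says "Hypotheses regarding the primary and secondary effectiveness outcomes are described below in Section 12.6". The text of Section 12.6 is not in the supplied document.

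**The concern.** Three features of the rule are unsatisfactory.

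1. The form of the primary model is settled by a test on the outcome. Whether center is adjusted for should be fixed in advance.
2. The trigger and the response do not match. A significant interaction says that the treatment effect varies between centers. A center main effect lets only the mean outcome vary.
3. A likelihood ratio test of many fixed effects under maximum likelihood, referred to chi-square, rejects too often in a sample of this size. The stated 0.15 would then not be the level at which the rule operates.

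At stake are a fully pre-specified primary model for a regulatory submission and a correct standard error if sites differ. Planned TBUT power and inflation of the TBUT type I error are not at stake on the plain reading.

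**Working it through.** **Inputs.** 200 randomized, 100 per arm (Protocol 12.7); 10% loss, so n = 180 (SAP 23.2.1); C = 5 to 15 centers (Protocol 7.3); TBUT change 4 s (SD 2) against 6 s (SD 3) (SAP 23.2.1); OSDI 10 against 18.5 points, SD 18 (SAP 23.2.2). The documents give no site variance, so shares of 0.1 and 0.2 of the total are assumed.

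**Planning power first.** The design effect is not visible, so take fully correlated eyes as the extreme. With 90 per arm, SE = √(4/90 + 9/90) = 0.380 s, 2/0.380 = 5.26, and power is about 99.95%. The plan's claim of more than 90% for TBUT is reproduced with much to spare.

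**Level of the screen.** Put center main effects in both models. The interaction has q = C − 1 degrees of freedom and the larger model has p = 2C + 1 parameters. At subject level the likelihood ratio statistic is n·log(1 + qF/(n − p)). Rejecting when it exceeds c, the 0.85 chi-square quantile on q degrees of freedom, has true level

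P{F(q, n − p) > ((n − p)/q)·(exp(c/n) − 1)}.

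| C | q | n − p | c | F threshold | True level |
|---|---|---|---|---|---|
| 5 | 4 | 169 | 6.74 | 1.613 | 0.173 |
| 10 | 9 | 159 | 13.29 | 1.354 | 0.214 |
| 15 | 14 | 149 | 19.41 | 1.212 | 0.273 |

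With all 200 subjects the levels are 0.171, 0.207 and 0.258. Simulation of the two-eye random-intercept model fitted by maximum likelihood, over several assumed between-eye correlations, agrees: 0.16–0.18, 0.20–0.22 and 0.26–0.29.

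The level also depends on how the test is built. If interaction terms are added to the printed model without center main effects, the screen fires in 16–20% of simulated trials with equal SDs. With the planned SDs of 2 and 3 it fires in 31–55%, with no center differences at all.

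**Effect of an F reference.** At n = 180 the critical value moves from 6.74 to 7.14, from 13.29 to 14.72 and from 19.41 to 22.55. Simulated levels are then 0.156 (5 centers) and 0.137 (15 centers).

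**Consequence for the TBUT test.** Subject-level simulation: blocks of 2 or 4, 10% random loss, SDs 2 and 3, 12,000 runs per cell, 5 and 15 centers, lists by site, pooled coefficient read at the end. Type I error:

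| Assumed site share | Center omitted | Two-stage rule | Center always in |
|---|---|---|---|
| 0 | 5.0–5.2% | 5.0–5.2% | 5.0–5.3% |
| 0.1 | 4.3% | 4.5% | 5.0–5.3% |
| 0.2 | 3.3–3.5% | 3.8–3.9% | 5.0–5.3% |

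With one list for all sites, omitting center gives 4.7–5.2% and the two-stage rule 4.8–5.2%.

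**Why omission is conservative with lists by site.** Adding center lowers the reported SE by about 4% and 9% at shares 0.1 and 0.2, but the true sampling SD by only about 0.3% and 1.1%. Without center, reported SE over true SD is therefore 0.997/0.96 = 1.039 and 0.989/0.91 = 1.087. Then 2·(1 − Φ(1.96 × 1.039)) = 4.2% and 2·(1 − Φ(1.96 × 1.087)) = 3.3%, in line with the simulation.

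**The case against.** The best defense is that 0.15 governs a poolability screen, not the effectiveness test. If the screen fires too often, it errs toward showing by-center results. On the plain reading, center is added as a main effect, the treatment coefficient remains one overall effect, and by-center results are reporting only. Little is then lost, and omitting center is at worst conservative. The SAP also names no reference distribution, so an F or bootstrap reference would remove the excess. Up to 15 centers is a maximum and small centers are merged, so 0.27 is the upper end. All of this stands, and it limits the point to specification and efficiency.

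A reader might go further. Since 23.1.1 says "T_i is the 0,1 treatment indicator for subject i", keeping the interaction in the model with 0/1 center indicators would turn the treatment coefficient into one reference center's effect. Alternatively, the by-center results might be taken to decide success. Either would reduce power and could change the conclusion. No visible passage says that the interaction is kept or that by-center results decide, and Section 12.6 may settle the matter, so no loss is claimed on those readings.

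The defense does not remove the dependence of the primary model on outcome data, or the mismatch between an interaction trigger and a main-effect response.

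**Conclusion.** The concern holds in a limited form. The primary TBUT model is chosen by an outcome-based screen whose response does not address what the screen detects. With a chi-square reference, center main effects in both models and 180 completers, the screen's level is about 0.17, 0.21 and 0.27 for 5, 10 and 15 centers.

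It would be wrong to infer that the TBUT test itself runs above 5%. With a pooled coefficient, type I error stays at or below about 5% and planned power for a 2 s difference is not at risk. The practical loss is a standard error about 4% and 9% too wide at assumed site shares of 0.1 and 0.2, with actual levels of about 4.3% and 3.4% when center is omitted. This requires lists by site, which the protocol suggests but does not state, and centers that differ, for which the documents give no figure.

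**What to change.** Before the primary database lock, revise 12.5.3 and 23.1.1–23.1.2 as follows:
- Include center, with small centers combined, in the primary model whatever the interaction test shows.
- State that the pooled center-adjusted treatment coefficient decides TBUT, unless Section 12.6 already fixes the deciding estimate.
- Make the interaction test and by-center results supportive.
- Test the interaction with center main effects in both models and an F reference, so that 0.15 holds approximately.

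It would also help to state in 9.5.3 whether lists are by site. The 3- and 6-month TBUT tests in 12.5.6 would inherit the same model.

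**Cost.** No new data, and up to 14 degrees of freedom. If centers do not differ, the SE rises by 0.1–0.7% with lists by site, or 1.2% (5 centers) to 4.2% (15 centers) with one list. If OSDI uses the same model, which the visible text does not say, the single-list cost is about 1 to 3 points of power. With 90 per arm, SE = 18·√(2/90) = 2.68 and power is 88.6%; multiplying the SE by 1.012 or 1.042 gives 87.9% or 86.0%. If one list is used and centers do differ, center instead cuts the true TBUT sampling SD by about 1–3% and 6–8% at shares 0.1 and 0.2.

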23.1.3 MISSING DATA

Note that since the primary analysis uses maximum likelihood methods on the complete data then any MAR (missing at random) imputation model should provide essentially equivalent results. That is, the missing data are ignorable if they are MAR and we are using full maximum likelihood estimation. However, as a sensitivity analysis, missing data for the primary TBUT outcome at the 1 month time point will be imputed using baseline characteristics and 1-week outcomes. In this, we follow the advice in sections 2.8 and 2.10 of "Multiple Imputation and its Application" to use an imputation model that is more complex than the final analysis model. In order to carry out the imputations we will fit a linear model that predicts TBUT change at 4 weeks using TBUT at baseline and 1 week, along with other covariates, as predictors. Using predicted 4-week means and variances from this model we can create multiple imputations for the missing 4-week TBUT changes. Results from the multiple imputations will be combined using Rubin's method.

Further sensitivity analysis can be carried out by extending the mixed effects model for the primary analysis described above to also include repeated measurements across time for each patient and eye. Under this model we can carry out maximum likelihood estimation that allows for one of the two (Week 1, Week 4) measurements for each person to be missing.

⁵⁶ Carpenter, J., and Kenward, M. Multiple Imputation and its Application (2013), Wiley UK.

23.1.4 SECONDARY EFFECTIVENESS ENDPOINTS

If the primary endpoint is successful (if the null hypothesis for the primary endpoint is rejected) then the secondary endpoints will be tested using a hierarchical testing procedure as described in 12.5.5.

23.1.5 EVALUATION OF TREATMENT DURATION

If the primary endpoint is successful at the one month primary time point, then treatment duration will be evaluated via comparisons of treatment versus control change in TBUT at each of the 3- and 6-month time points separately as described in 12.5.6.

For each secondary endpoint that is successful at the one month time point using the hierarchical testing procedure described in 12.5.5, treatment duration will be evaluated at the 3- and 6-month follow up. Evaluation of treatment duration for the secondary endpoints will be based on sequential testing of 3- and 6-month follow up times separately, in the same manner as for the primary endpoint. Secondary endpoints that fail at the 1-month time point will not be evaluated for treatment duration

23.1.6 Modeling of Extended Follow-up Results

If the primary endpoint is successful at one month, then as a supplemental analysis we will fit linear mixed effects models to the 1-3- and 6-month longitudinal results.

The chosen model will allow us to evaluate the following:

- Maintenance of the Treatment effect using the full longitudinal data on each subject, providing some guide as to an appropriate retreatment schedule,
- A more detailed evaluation of the baseline effects, if any.

A summary of any model selection process, as well as more detailed output from the selected model, will be provided in the final report.

For the TearCare subjects only, the data from all visits out to 12 months will be used to further investigate the durability of the treatment effect. Similar LME modeling will allow us to evaluate their change from baseline out to 12 months. However since the Warm Compress group will crossover to TearCare at 6 months, there will be no control group to provide an unbiased comparison at the 7, 9 or 12 month points.

For the Warm Compress subjects who cross over, their combined 6 through 12-month data will be analyzed separately (again, using appropriate LME modeling) to evaluate their response to the cross over TearCare treatment. In this analysis their 6-month (precrossover) measurements will be used as the new "baseline" that will be used to compare with their 7-, 9- and 12-month outcomes. Again, there will be no control group for comparison.

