6 STUDY ENDPOINTS

6.1 EFFECTIVENESS ENDPOINTS

[figure not shown]
This study will collect data to assess the impact of each treatment on the signs and symptoms of dry eye disease. Tear Break-Up Time, which measures the treatment effect of the device on the signs of dry eye disease, is the primary endpoint. The Ocular Surface Disease Index (OSDI) questionnaire, which is a validated instrument for measuring the severity of symptoms of dry eye disease, is the key secondary endpoint. The following other secondary endpoints have been chosen to collect additional data regarding changes in the signs and symptoms of dry eye disease in study subjects: Meibomian Gland Secretion Score, Corneal and Conjunctival Staining, the Symptom Assessment in Dry Eye (SANDE) questionnaire, and the Eye Dryness Score.

For each outcome measure, results from the TearCare subjects will be compared with results from the Warm Compress and Lid Massage subjects. All the primary and secondary endpoints will be at 1 month.

- Primary effectiveness endpoint
 - Mean Change from baseline in Tear Break-Up Time (TBUT)
- Secondary effectiveness endpoints
 - Mean Change from baseline in OSDI score³⁹
 - Mean Change from baseline in the total Meibomian Gland Secretion Score 40
 - Mean Change from baseline in corneal staining scores
 - Mean Change from baseline in conjunctival staining scores
 - Mean Change from baseline in SANDE scores 41,42
 - Eye Dryness Score

• Treatment Duration Endpoints

- Mean 3- and 6-month Change from baseline for successful primary and secondary endpoints
- Additional Exploratory Endpoints

- Number of meibomian glands yielding clear liquid secretions
- Number of meibomian glands secreting any liquid (clear or cloudy)
- Use of dry eye lubricants
- Assessment of all effectiveness endpoints at 7, 9 and 12 months.

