9.2 NUMBER OF SUBJECTS, DURATION OF FOLLOW-UP AND STUDY DURATION

A total of 200 subjects will be enrolled and randomized in the study. Assuming a 15% screen failure rate, approximately 230 subjects will be enrolled and screened to obtain 200 randomized subjects. All subjects will be followed for 12 months.

It is anticipated that enrollment in the study will take 3-6 months. Including the 12-month follow-up period, the study is expected to last 15-18 months.

Analysis of the primary outcome will occur when the last subject has reached the 1 month follow up. In order to evaluate long-term results of the TearCare treatment, data will be re-analyzed after the last subject reaches the 6 month follow-up and then again after the last subject reaches the 12 month follow up.

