9.6 FOLLOW-UP VISITS

9.6.1 FOLLOW-UP VISIT ROUTINE PROCEDURES

Prior to the Visit: Reminder Call

A few days before the follow-up visit, it is recommended that the coordinator contact the subject to remind them to bring their unused Refresh Plus vials and, if they are in the warm compress group, their Warm Compress Log.

Also, since dry eye drops and lubricants can affect the endpoint assessments, it is important to remind subjects, on the day of the Follow-up visit, not to use any of these products before the Follow-up visit.

At the Beginning of the Follow-up Visit: Maintaining Masking of Study Personnel

Endpoint assessments performed during the Follow-up visit must be performed by the Masked Assessor (See Section 9.7).

At the beginning of the follow-up visit, the coordinator should remind the subject to not reveal their randomization group to the study personnel who will be performing the follow-up exams.

Order of Procedures During the Follow-Up Visit

Follow-up procedures will be performed per the Study Schedule provided in Table 3 (page 28) and the methods included in Appendix A. Since certain tests/exams can impact the ability to perform other tests/exams, the following tests and exams should be performed in this order:

- 1. Questionnaires
- 2. Manifest refraction and ETDRS Best-corrected visual acuity
- 3. Slit Lamp Exam
- 4. Tear Breakup Time
- 5. Corneal and conjunctival staining score
- 6. Meibomian Gland Secretion Scoring

CONFIDENTIAL Sight Sciences

- 7. IOP
- Assessment of adverse events

The following activities can be performed in any order:

- Medication Use
- Collection of Warm Compress Log
- · Count unused Refresh Plus Vials

At the End of the Follow-Up Visit

At the end of the follow-up visit, provide subjects with a new supply of Refresh Plus vials, if needed. Record how many vials are provided to the subject.

For subjects in the Warm Compress and Lid Massage group, provide them with a new Warm Compress Log for use in the next follow-up period.

9.6.2 6 Month Follow-up Visit: Re-Treatment

Scheduling the 6 Month Visit

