9.7 MASKED ASSESSOR

To reduce potential bias in the study, study staff performing endpoint assessments will be masked as to the subject's treatment arm. In addition, to ensure consistency in performing the endpoint assessments the study staff member who performs the baseline assessments should also perform the follow-up assessments. An alternate Masked Assessor may be appointed to handle scheduling conflicts, but every effort should be made to have the same person performing all endpoint assessments throughout the study. The Masked Assessor should not perform the randomization, inoffice TearCare Treatment, gland expression or the in-office warm compress treatment prior to home use. Masking will be maintained until all subjects at the site have passed the 6-month follow up time.

The following assessments must be performed by Masked Assessor:

- Manifest refraction and BCVA
- Slit lamp exam
- Tear Break-up Time
- Corneal and conjunctival staining
- Meibomian gland secretion scoring
- IOP
- AE assessment

The study coordinator should collect the Warm Compress Log from the subject.

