12.5.8 Modeling of Extended Follow-up Results

After the initial 1 month primary analysis, subjects will be followed up to 12 months to evaluate durability of the treatment effect. After the 6 month visit, subjects in the Warm Compress group will cross over into the TearCare arm. Treatment duration will be evaluated primarily via comparisons of treatment versus control change in TBUT at each of the 3- and 6-month time points separately as described in 12.5.6.

[figure not shown]
After 6- and 12-month follow-up is complete the longitudinal study data will be reanalyzed, again using LME modeling methods. These models will allow us to evaluate the following:

- Maintenance of the Treatment effect using the full longitudinal data on each subject,
- A more detailed evaluation of the baseline effects, if any.

At the 12 month follow-up the Warm Compress subjects will have received TearCare treatment at 6 months, thus we will lose a comparison to randomized control subjects at this point. However for those subjects who receive TearCare at 6 months we will be able to carry out a before- versus after- TearCare comparison, which may provide useful supplementary information.

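### Assessor masking to arm is guaranteed only until a site's last subject passes month 6, so the supplementary analyses out to month 12 may compare masked reference readings with later readings taken with the original arm known

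*Combined protocol and SAP*

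**What the plan says.** - **How long masking lasts.** Protocol Section 9.7 is the one place that sets a duration: "Masking will be maintained until all subjects at the site have passed the 6-month follow up time". Section 12.5.6, on treatment duration, repeats the limit: "every effort will be made to maintain the masking of assessors through the 6-month follow-up as described in section 9.7".
- **Who assesses follow-up visits.** Section 9.6.1 states: "Endpoint assessments performed during the Follow-up visit must be performed by the Masked Assessor (See Section 9.7". It gives no end date of its own and points to Section 9.7.
- **What happens at month 6.** Section 12.5.8 states: "After the 6 month visit, subjects in the Warm Compress group will cross over into the TearCare arm". Under Section 9.6.2 the TearCare arm is re-treated once its month-6 exams are done. Both arms therefore receive TearCare at about month 6.
- **What is analyzed afterwards.** In SAP Section 23.1.6, for the crossed-over controls, "their 6-month (precrossover) measurements will be used as the new" baseline against which months 7, 9 and 12 are compared. For the TearCare arm the same section says: "Similar LME modeling will allow us to evaluate their change from baseline out to 12 months". Section 6.1 lists among the exploratory endpoints: "Assessment of all effectiveness endpoints at 7, 9 and 12 months".
- **What the plan concedes.** Sections 12.5.8 and 23.1.6 say that there is no randomized control after month 6, and Section 12.5.8 treats the before-after comparison as supplementary. Neither mentions that the masking guarantee may have ended for the later readings.

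**The concern.** Section 7 relies on masked assessors to limit bias, because subjects cannot be masked. TBUT, corneal and conjunctival staining, and meibomian gland scores are read by an assessor and leave room for judgment. A before-after contrast is easiest to interpret when both readings are taken under the same conditions. Here the reference reading is always inside the masking guarantee and the later reading may not be. Part of an observed change could then reflect what the assessor knew about the subject's original arm.

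The crossover response and the TearCare arm's durability out to 12 months are at stake. The patient-reported outcomes (OSDI, SANDE, Eye Dryness Score) are not: subjects complete those questionnaires themselves and know their treatment throughout.

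**Working it through.** The plan states no figure on this point, so there is none to reproduce. The check asks which readings fall inside the guarantee.

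**Inputs**
- The guarantee ends, site by site, when the last subject passes month 6 (Section 9.7).
- Reference readings are month 6 for crossed-over controls and baseline for the TearCare arm. Later readings for both are at months 7, 9 and 12 (Section 23.1.6).
- On the enrollment window, Section 9.2 says: "It is anticipated that enrollment in the study will take 3-6 months". That is for the whole study. No window for a single site is given, so the site window E is an assumption.

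**Formula.** Let a site enroll over E months, with a subject entering at time u between 0 and E, and take nominal visit dates. The guarantee ends at time E + 6. A month-m visit takes place at u + m and is outside the guarantee if u + m > E + 6. This holds for subjects who entered in the last fraction x = min(1, (m − 6)/E) of the window. With uniform enrollment the share of visits outside is x.

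**Reference readings.** At month 6, u + 6 never exceeds E + 6, so the share outside is 0%. The TearCare arm's baseline is earlier still, so it is also 0%.

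**Later readings, uniform enrollment**

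| Assumed site window E | Month 7: 1/E | Month 9: 3/E | Month 12: 6/E |
|---|---|---|---|
| 6 months | 1/6 = 17% | 3/6 = 50% | 6/6 = 100% |
| 3 months | 1/3 = 33% | 100% (capped) | 100% (capped) |
| 2 months | 1/2 = 50% | 100% (capped) | 100% (capped) |
| 1 month | 100% | 100% (capped) | 100% (capped) |

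**Sensitivity to enrollment pattern.** If enrollment falls linearly to zero, the share is x². If it rises linearly from zero, the share is 1 − (1 − x)².
- E = 6, month 7: (1/6)² = 3% falling, 1 − (5/6)² = 31% rising.
- E = 6, month 9: (1/2)² = 25% falling, 1 − (1/2)² = 75% rising.
- E = 3, month 7: (1/3)² = 11% falling, 1 − (2/3)² = 56% rising.
- E = 3, month 9: 100% under either pattern.

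**What is firm.** For any E of 6 months or less, x = 1 at month 12, so the share is 100% whatever the pattern. A site cannot enroll for longer than the study does, so this follows for every site if the anticipated study-wide window holds. The month 7 and month 9 shares vary widely and serve only as illustration.

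These are shares of visits outside the guarantee. They are not shares known to be unmasked.

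**The case against.** **Masking may continue in practice.** Section 9.6.1 and Appendix A call for a masked assessor with no end date. Section 9.7 keeps that person away from randomization and treatment and asks for the same person throughout. The pointer in 9.6.1 could be read as identifying the role rather than importing the end date. This stands in part: nothing says that assignments will be released. But 9.7 is the only text that says how long masking lasts, and a site could let it lapse after its last month-6 visit and still comply. Some relevant text is also not visible (the study schedule in Table 3 and the synopsis entry for the control treatment), so it cannot be ruled out that assessor handling around the crossover is described there.

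**Masking to arm does little here.** Both arms have just had TearCare, so an assessor masked to arm still knows that each month 7-12 reading follows treatment. This stands and limits the value of any fix. Masking would hide only whether that treatment was a first one or a re-treatment.

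**The analysis is already caveated.** The plan says that it is uncontrolled and supplementary. That is true, but a missing control group is a different limitation from a change in how the readings are taken.

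**Stronger readings that the documents do not support**
- A reader might infer a biased comparison between arms after month 6. Section 23.1.6 analyzes the two groups separately, each against its own reference, and plans no formal between-arm comparison at those visits.
- A reader might infer that no later analysis could help. Where some month 7 and month 9 readings remain inside the guarantee, results could be examined by whether the visit preceded the end of masking at the site. That check is partial: inside-versus-outside status follows enrollment order, and none is available at month 12 if the site enrolled within 6 months.
- A reader might turn the shares into a count of affected visits. That would need site windows, retention and crossover uptake that the documents do not give.

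**Conclusion.** The point holds as a limited gap in the supplementary analyses and is worth considering. Every reference reading is inside the masking guarantee. Every month-12 reading is outside it at any site that enrolls within 6 months, and an unknown share is outside at months 7 and 9. Section 23.1.6 does not tell the reader this.

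The gap is confined to assessor-read outcomes in the two within-arm analyses and to the exploratory month 7, 9 and 12 endpoints that use the same readings. The primary endpoint, the 1-month secondary endpoints and the 3- and 6-month duration tests all use readings inside the guarantee. The conclusion assumes nominal visit dates and that Section 9.7 governs the duration of masking. It does not assume that assessors will in fact be told assignments, and the documents give no basis for estimating a bias.

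**What to change.** In Section 9.7, replace the month-6 end point with month 12, so that assessors stay masked to original arm until the site's last subject has completed the month 12 visit. In Section 23.1.6, add one sentence saying that assessors will still know that readings after month 6 follow TearCare, so before-after expectation is reduced but not removed.

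The cost is small: one visit changed and one sentence added, with no new visits, data, staff or subjects, because the masked assessor role already exists. The downside is that sites must keep that assessor apart from randomization and treatment records for up to six more months (12 − 6). If the sponsor prefers not to extend masking, the sentence in 23.1.6 should instead say that the guarantee ends at month 6 and that later assessor-read outcomes may have been taken with the original arm known.
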